Cover page

Title: Neuromodulation Using Vagus Nerve Stimulation Following Ischemic Stroke as

Therapeutic Adjunct (NUVISTA)

NCT number: NCT05390580, Approval Date: 2/4/2025

Study Title: Vagus Nerve Stimulation following a Large Vessel Occlusion Acute Ischemic Stroke

(NUVISTA)

Principal Investigator: [name] MD

Co-investigator(s): [name] [name]; [name] MD

Sponsor or funding source: None

Objectives

To quantify inflammatory markers in the blood of patients who present with ischemic strokes due to large vessel occlusions to Barnes Jewish Hospital, and determine if treatment with auricular transcutaneous vagal nerve stimulation alters the levels of inflammatory markers in these patients over time, and we will explore if it impacts their overall outcome.

Methods and Measures

Design

This is a randomized open-label, with blinded outcome pilot study to evaluate the effect on inflammatory laboratory values and explore clinical outcomes in patients who present with ischemic strokes due to large vessel occlusions and are treated with either current accepted management, or accepted management in addition to transcutaneous auricular vagal nerve stimulation.

Setting

Patients in this study will be inpatient at Barnes Jewish Hospital

Data Collection Criteria

Adult patients who present with acute ischemic strokes due to large vessel occlusions to Barnes Jewish Hospital will be considered for enrollment in this study. Exclusion criteria will include patients <18 years old, patients with presumed chronic large vessel occlusions, posterior circulation LVOs, NIHSS<6, CTP Penumbra <1/3 total ischemic area, pre-morbid modified Rankin score (mRS) >2, unable to initiate treatment under 36 hours from symptom discovery, life expectancy <3 months, patients' undergoing active cancer or immunosuppressive/modulating therapy, or patients with sustained bradycardia on arrival with a heart rate <50 beats per minute.

Sample size

We anticipate enrolling approximately 80 patients into the study, with random assortment to treatment with standard medical care, and standard medical care with transcutaneous auricular vagal nerve stimulation.

Intervention

Patients enrolled in the trial will be randomized to treatment with or without electrical stimulation via an auricular, transcutaneous vagus nerve stimulator. All patients will be fitted with the device, we will attach adhesive contacts to the left ear. Stimulation sessions will occur for 20 minutes twice daily during the inpatient period. Patients assigned to the controls arm will have no electricity applied,

those treated with stimulation will be treated with the following parameters: frequency 20 Hz, pulse width 250 μ m, and varying intensities from 0.4 mA to 2 mA (intensity is always titrated to be a level below painful threshold in a patient). The amplitude of stimulation may be reduced if a patient complains of discomfort at the site of stimulation. The site of stimulation will be inspected daily before and after treatment to ensure there is no redness or irritation at the site.

Outcome Measure(s)

The primary endpoints of the study will be changes in the levels of inflammatory markers that include IL-1b, IL-6, TNF-α, and white blood cell count in the blood, as well as specific inflammatory cell counts (neutrophil to lymphocyte ratio, for example) at time of admission, and every day throughout the hospitalization. The secondary exploratory endpoints will be clinical outcomes assessed via the change in daily NIHSS and mRS at 30 and 90 days, as well as safety endpoints with regards to blood pressure and heart rate. We will also do mononuclear cell genetic testing to attempt to identify phenotypes that respond to the intervention. Follow up data will be obtained via chart review, we will obtain the mRS data at 30 days over the phone, and we will make additional outpatient follow up appointments for the research study in order to collect the NIHSS and mRS data at 90 days.

Analytical Plan

Results will be analyzed initially using descriptive statistics. Comparison between groups will be done using chi square tests for proportions, and t-tests or ANOVA procedures for continuous variables. Regression analysis will be performed to identify independent outcome predictors. Other inferential statistical analysis will be conducted as appropriate. Please see document with statistical plan that is attached.

Human Subjects Protection

Subject Recruitment Methods

Intensive care unit staff as well as physicians in the Department of Neurology will be made aware of this study, and be directed to notify the research group when a patient presents with an ischemic stroke due to a large vessel occlusion. The research team will then screen the patients to see if they are eligible for enrollment in the study. Additional patient data, including medical history, laboratory values, and clinical assessments will be obtained from the electronic health records.

Informed Consent

Informed consent will be obtained from the patient if they are able, or from the appropriate party that is providing consent for their medical care if they are unable to provide consent. A copy of the paper consent is also submitted.

Confidentiality and Privacy

Confidentiality will be protected by collecting only information needed to assess study outcomes, and maintaining all study information in a secure manner. Data will be de-identified and stored with an assigned ID number. Data access will be limited to study staff. Data and records will be kept locked and secured, with any computer data password protected. No reference to any individual participant will appear in reports, presentations, or publications that may arise from the study.

Data and Safety Monitoring

The principal investigator will be responsible for the overall monitoring of the data and safety of study participants. The principal investigator will be assisted by other members of the study staff.

Reporting of Unanticipated Problems, Adverse Events or Deviations

Any unanticipated problems, serious and unexpected adverse events, deviations or protocol changes will be promptly reported by the principal investigator or designated member of the research team to the IRB and sponsor or appropriate government agency if appropriate.

Abbreviations:

ANOVA: Analysis of variance

AIS: Acute Ischemic Stroke

CRP: C-Reactive Protein

CT: Computerized Tomography

ID: Identification Number

IFN: Interferon

IL: Interleukin

LVO: Large Vessel Occlusion

MRI: Magnetic Resonance Imaging

NIHSS: National Institute of Health Stroke Scale

TAVNS: transcutaneous auricular Vagal Nerve Stimulator

TGF: Transforming growth factor

TNF: Tumor Necrosis Factor

VNS: Vagal Nerver Stimulator

Expanded Statistical Analysis:

Statistical analysis.

Statistical analyses were performed using Stata/MP version 18 (StataCorp LLC 2023, Statistical Software, College Station, TX) and Python packages Scipy and Statsmodels. All continuous variables were retained as continuous, except where noted. Multivariable regression was used to examine treatment group associations with outcomes, except for rare secondary outcomes/adverse effects. Following FDA recommendations, an intention-to-treat (ITT) approach was implemented. Primary ITT analyses were conducted without transformation of continuous outcome variables because ≥35 observations were available.

Statistical analysis of rate of change in cytokines, WBC, and neurological outcomes in taVNS vs. sham treatment.

Longitudinal data were analyzed using mixed effects models per the FDA, with person as a random effect, given multiple records per person. For cytokine models, assay plate was included as an additional random effect. This approach accommodated irregularly timed points, less restrictive missing data assumptions, and time-varying variables. To complement our primary ITT approach, treatment also was handled as time-varying when noted, with assignment occurring at randomization. All longitudinal models included treatment, time since LKN, and their interaction term(s) as primary independent variables to test whether the pattern of change over time differed between the taVNS and sham groups. Time was modeled quadratically for cytokine and WBC outcomes to capture the known U-shaped associations with time when modeling these outcomes and linearly for in-hospital NIHSS scores based on panel data plots. For NIHSS, a single model was constructed to estimate the rate of change (change in NIHSS per

day) in each of the two treatment groups and to formally test whether these rates were different. For 30-day NIHSS changes (vs. baseline) and 90-day mRS changes, we used the parallel model, with actual assessment days scaled to standardize the evaluation period to 30 or 90 days, respectively. We characterized the daily change in each WBC or cytokine outcome using a similar model expanded to include the quadratic terms. Treatment-time interactions were tested using likelihood ratio tests comparing models with and without interaction term (NIHSS, mRS) or terms (cytokines, WBC), with significance at two-sided α =0.05. These analyses were adjusted for baseline covariates, including baseline NIHSS (except in NIHSS models, which included this observation), time from LKN to thrombus removal time or recanalization attempt (groin puncture time), and percent reperfusion (0-100%) based on TICI score to obtain a single semicontinuous measure. In sensitivity analyses, we also performed the analysis with a dichotomized TICI scale (reperfused ≥2B, not reperfused <2B) or restricted data to the first five days post-LKN (when most stimulations and hospitalizations had ended). Finally, we explored whether any difference in longitudinal patterns between taVNS and sham depended any of the a priori adjustment variables, i.e., whether any time-treatment interaction depended on one of these three variables. We conducted post-hoc t-tests to compare cytokine levels between groups on each day.

Statistical analysis of safety and exploratory analysis of the Stroke Complications and Poor Outcomes in relation to treatment.

To assess our dichotomous safety endpoints, we used logistic regression models constructed to assess differences in bradycardia, hypotension, infection, hemicraniectomy, hemorrhagic transformation, and deaths amongst treated vs non-treated patients. To explore the hypothesis that taVNS reduces the incidence of complications and poor outcomes, we performed logistic

regression models for discharge related outcomes, defined as: readmission, length of stay, and hospital poor disposition (i.e. nursing home, long-term acute care hospital, or death).

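### The stimulation site is inspected daily and discomfort can lower the amplitude, but the plan makes no commitment to record, summarise or compare these local effects

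*Combined protocol and SAP*

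**What the plan says.** Three parts of the document bear on this.

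- **Protocol, Intervention.** Both arms wear the device: "All patients will be fitted with the device, we will attach adhesive contacts to the left ear". Controls receive no current. Skin at the site is checked: "The site of stimulation will be inspected daily before and after treatment to ensure there is no redness or irritation at the site". Discomfort can change what is delivered: "The amplitude of stimulation may be reduced if a patient complains of discomfort at the site of stimulation".
- **Protocol, Outcome Measure(s).** Safety enters among the secondary exploratory endpoints, "as well as safety endpoints with regards to blood pressure and heart rate". No local effect is named.
- **SAP (Expanded Statistical Analysis), safety paragraph.** Logistic regression is planned for "differences in bradycardia, hypotension, infection, hemicraniectomy, hemorrhagic transformation, and deaths amongst treated vs non-treated patients". The exploratory outcomes that follow are readmission, length of stay and poor disposition.

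Two other statements touch on harms in general terms. The protocol's adverse event section says "Any unanticipated problems, serious and unexpected adverse events, deviations or protocol changes will be promptly reported". The SAP's opening paragraph uses multivariable regression "except for rare secondary outcomes/adverse effects", without listing those effects or giving another method for them.

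**The concern.** The protocol recognises two local effects of the device, skin reaction and discomfort, and has staff look for one and respond to the other. Neither is carried into an endpoint or a named summary. Four of the six SAP safety endpoints (infection, hemicraniectomy, hemorrhagic transformation, death) can arise from the stroke itself. Bradycardia and hypotension address possible systemic effects of vagal stimulation. What happens at the ear is not covered.

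For a device pilot, the local tolerability rate is among the results that a later trial would want. The design is also well placed to supply it, because both arms wear adhesive contacts and only one receives current. Amplitude reductions matter for a second reason: intensity may range from 0.4 to 2 mA, so reductions describe the stimulation actually delivered when the biomarker results are read.

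**Working it through.** The plan gives no figure on local events, so there is none to reproduce. The check has two parts.

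**1. Is each local effect carried into the analysis?**

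| Local effect | Observed or acted on (Intervention) | Protocol safety endpoints | SAP safety list | SAP exploratory list |
|---|---|---|---|---|
| Redness or irritation | Yes, daily inspection | No | No | No |
| Discomfort | Yes, on complaint | No | No | No |
| Amplitude reduction | Yes, permitted | No | No | No |

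The adverse event section covers unanticipated problems and events that are serious and unexpected. A mild skin reaction that the protocol already screens for does not clearly fall under either. The SAP's single mention of adverse effects names none. The protocol's Analytical Plan promises descriptive statistics and chi-square tests, but attaches them to no local variable.

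**2. Would a count be informative at this size?**

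Inputs: "We anticipate enrolling approximately 80 patients into the study". The allocation ratio is not stated, so 40 per arm is an assumption, with 35 to 45 as a range. All event rates below are assumptions, because the documents give none.

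*Exact two-sided 95% upper limit with no events in n patients:* 1 − 0.025^(1/n).

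- n = 35: 1 − 0.025^(1/35) = 10.0%
- n = 40: 1 − 0.025^(1/40) = 8.8%
- n = 45: 1 − 0.025^(1/45) = 7.9%

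*Chance of at least one case in n patients at true rate p:* 1 − (1 − p)^n.

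| True rate | n = 35 | n = 40 | n = 45 |
|---|---|---|---|
| 2% | 51% | 55% | 60% |
| 5% | 83% | 87% | 90% |
| 10% | 97.5% | 98.5% | 99.1% |

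If the rate is 5% or more, the pilot will probably see cases. If it sees none, it can exclude rates above about 8% to 10%.

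*What a between-arm comparison could show.* Take rates of 20% and 5% for illustration: 40 × 0.20 = 8 and 40 × 0.05 = 2 affected patients.

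- Exact 95% interval for 8/40: 9% to 36%
- Exact 95% interval for 2/40: 0.6% to 17%
- Fisher's exact test, 8/40 against 2/40: p = 0.087
- Power of Fisher's test at two-sided 5% with 40 per arm: about 41% for 20% v 5%, and about 18% for 15% v 5%

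The per-arm estimates are useful. A significance test is not a sound basis for a conclusion.

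**The case against.** The strongest reply is that absence from a list of modelled outcomes is not a decision to leave something unreported. The SAP paragraph names what goes into logistic regression and does not say that nothing else will be tabulated. A by-arm count of skin reactions would fit the Analytical Plan's general wording, and the SAP contemplates adverse effects outside its multivariable models. A serious and unexpected local injury would go to the IRB. No case report form is in the documents, so whether the inspections are charted is unknown.

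Much of this stands. A reader might infer that the SAP's list is closed, that local effects would be reported nowhere, or that the trial would claim safety without them. The documents support none of these. They forbid no reporting, they make no safety claim, and the stated objective concerns inflammatory markers. What remains is narrower: permissive general wording is not a commitment, and no sentence commits the trial to an estimate.

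The comparison itself also has limits, and these stand too:

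- Power is low, as shown above.
- The design is open-label and nothing says that the person inspecting the ear is blinded, so a difference in redness could reflect observer bias. A reader might infer that comparing the arms would cleanly separate the effect of current from that of adhesive; at this size and without blinded inspection, it would not.
- Sessions are twice daily but the inspection is described as daily, so per-session data are not assured. Inspection of control ears is not stated explicitly.
- Intensity is always titrated to stay below the pain threshold, and no rule separates routine titration from a reduction made for discomfort.
- The SAP is written in the past tense, so a new recorded item may come too late.

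**Conclusion.** The point holds as a gap in planned harms reporting. The protocol has the stimulation site inspected and allows amplitude to be reduced for discomfort, but no safety endpoint in the protocol or SAP includes a local or device tolerability event, and nothing commits the trial to recording, summarising or comparing them.

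The size can be given only as what a count would deliver. Zero cases would bound the rate at 8.8% with an assumed 40 per arm (10.0% to 7.9% for 35 to 45). At an assumed true rate of 5%, at least one case would be seen with probability 87% (83% to 90%). The primary biomarker result is unaffected, and the plan contains no contradiction on this point. It is a cheap improvement worth making, because it changes what the pilot can say about tolerability.

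**What to change.** Add two items to the SAP safety paragraph. They concern reporting only and leave the stimulation rules as they are.

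- **(a) Site reaction, both arms.** The number and percentage of patients in each arm with any new redness or irritation at the site, using the same inspection in sham and taVNS patients. Give exact 95% confidence intervals and show the between-arm difference as descriptive.
- **(b) Amplitude reduction, taVNS arm only.** The number and percentage of patients with any reduction recorded as due to discomfort, with an exact 95% interval. Recording the reason keeps these apart from routine titration.

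Count patients rather than sessions, since per-session inspection is not assured. Say whether the inspector knew the allocation.

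The cost is one extra recorded item alongside an inspection already required, plus a short table; no added visits or procedures are needed. The downsides are low power for any between-arm test and possible observer bias, and both should be acknowledged beside the result. If data collection is complete, the analysis depends on what was charted. If inspections or reasons for reduction were not charted, say so as a limitation.

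### The only analysis the SAP names for blood pressure and heart rate is of yes/no hypotension and bradycardia; an added continuous comparison would show a modest shift more often, at little cost

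*Combined protocol and SAP*

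**What the plan says.** Under Outcome Measure(s), the protocol includes among its secondary exploratory endpoints "safety endpoints with regards to blood pressure and heart rate". It gives no summary measure, timing or threshold.

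The safety subsection of the Expanded Statistical Analysis takes these up as yes/no events: "To assess our dichotomous safety endpoints, we used logistic regression models constructed to assess differences in bradycardia, hypotension, infection, hemicraniectomy, hemorrhagic transformation, and deaths". Bradycardia and hypotension are not defined there. The only heart-rate figure in the documents, below 50 beats/min on arrival, is an exclusion criterion.

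Four other statements bear on the point:
- The Analytical Plan gives a general provision for "t-tests or ANOVA procedures for continuous variables" and then refers the reader to the attached statistical plan. It does not mention blood pressure or heart rate.
- The Expanded Statistical Analysis says "All continuous variables were retained as continuous, except where noted".
- It uses multivariable regression "except for rare secondary outcomes/adverse effects", and names no alternative for those outcomes.
- The mixed models come under the heading "Statistical analysis of rate of change in cytokines, WBC, and neurological outcomes in taVNS vs. sham treatment". Vital signs are not among the outcomes modelled.

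On size, the protocol says "We anticipate enrolling approximately 80 patients into the study". It gives no allocation ratio and no power for any safety endpoint.

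**The concern.** Heart rate and blood pressure are measured on a continuous scale. Reducing each to whether a threshold was crossed discards how far every other patient moved. In a pilot of about 80 patients this matters, because a modest haemodynamic effect of vagal stimulation could be present and still leave the event comparison non-significant. If few patients cross the threshold, an arm may have no events, and the logistic model then has no finite odds ratio to report. At stake is what the pilot can say about haemodynamic effect: an odds ratio with a very wide interval, or none at all, tells later work little about what has been excluded.

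**Working it through.** The documents give no power, event rate, SD or effect size for these endpoints, so there is no planned figure to reproduce. What follows is illustrative.

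**Inputs**
- Total of about 80: protocol, Sample size.
- 40 per arm: assumes 1:1 allocation.
- Two-sided α = 0.05: stated for the treatment-time interaction tests, assumed here for safety.
- Lowest heart rate per patient: normal, SD 12, control mean μ of 60 to 75 (assumed).
- Cut-off of 50: borrowed from the arrival exclusion for illustration only. It is not an endpoint definition in the documents.
- True fall of 6 beats/min, so d = 6/12 = 0.5 SD (assumed).

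**Event rates.** Control: p0 = Φ((50 − μ)/12). Stimulation: p1 = Φ((50 − (μ − 6))/12). For μ = 70, p0 = Φ(−1.667) = 4.8% and p1 = Φ(−1.167) = 12.2%.

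**Yes/no power.** All pairs of binomial counts (40 per arm) are enumerated, and the probabilities of the tables that reject are summed. The tests are the unadjusted logistic likelihood ratio test and, for comparison, Fisher's exact test.

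**Chance that at least one arm has no events.** 1 − [1 − (1 − p0)^40] × [1 − (1 − p1)^40]. For μ = 70: (1 − p0)^40 = 0.141 and (1 − p1)^40 = 0.0056, so 1 − 0.859 × 0.9944 = 0.146.

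| Mean lowest rate μ | p0 vs p1 | Likelihood ratio power | Fisher power | An arm with no events |
|---|---|---|---|---|
| 60 | 20.2% vs 36.9% | 40% | 30% | under 0.1% |
| 65 | 10.6% vs 22.7% | 31% | 22% | 1% |
| 70 | 4.8% vs 12.2% | 26% | 10% | 15% |
| 75 | 1.9% vs 5.7% | 20% | 1% | 52% |

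**Continuous power, one value per patient.** Two-sample t-test, 78 degrees of freedom, noncentrality d × √(40/2) = 0.5 × 4.472 = 2.236. Power is 59.8%.

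**Other effect sizes**
- At 0.3 and 0.4 SD the t-test has 26% and 42% power, so small shifts are usually missed even when kept continuous.
- At 0.8 to 1.0 SD the likelihood ratio test has 57% to 79% power at μ = 70, 70% to 94% at μ of 60 to 65, and roughly 45% to 64% at μ = 75. The t-test has 94% to 99%.

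**Check without heart-rate units.** This version applies equally to blood pressure. Take a control event rate p0, shift the underlying normal variable by d = 0.5, and set p1 = Φ(Φ⁻¹(p0) + 0.5). For p0 = 5%, 10% and 20%, p1 = 12.6%, 21.7% and 36.6%. By the normal approximation, yes/no power is 22%, 30% and 38%, against 61% for comparing means.

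**The case against.** **A continuous comparison is not excluded.** The Analytical Plan's general line on continuous variables could cover vital signs. This stands: the gap is that no such analysis is named for blood pressure or heart rate and no summary is chosen, so the choice stays open until the data are seen.

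**No rule is broken.** A reader might infer that dichotomising contradicts the SAP's statement about continuous variables. It does not. That statement allows noted exceptions, and the safety subsection calls these endpoints dichotomous.

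**Not every real effect would be missed.** A reader might infer that a haemodynamic effect would usually go undetected whatever its size. The documents supply none of the inputs for that, and the calculation shows it fails for large shifts in most scenarios. The pilot's size also limits the continuous test.

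**Rare events are partly foreseen.** The SAP exempts rare adverse effects from multivariable regression. But it names no alternative and still lists logistic regression for every dichotomous safety endpoint. An empty arm does not stop a likelihood ratio test from giving a p-value; it is the odds ratio that has no finite estimate. At μ = 75, nearly all of the 20% power comes from such tables: without them about 1% remains.

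**Threshold events have their own value.** A bradycardia event and a small mean fall answer different safety questions. This stands, and it is why the continuous analysis should be added and need not replace the events or become the main safety result.

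**Nothing says a null result will be called safe.** Correct. The documents describe a pilot with exploratory endpoints. The caution about interpretation is a safeguard, not a correction of a stated claim.

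**Conclusion.** The point holds as a cheap improvement to an exploratory safety analysis. The plan names blood pressure and heart rate as endpoints, but the only analysis it names for them is of yes/no events. For a 0.5 SD fall in heart rate, that choice lowers power from about 60% to about 20% to 40%, and the unit-free check gives a similar loss that would apply to blood pressure. An arm with no events has a chance of about 15% to 52% if the mean lowest rate is 70 to 75, and about 1% or less if it is 60 to 65.

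These sizes rest on 1:1 allocation, normality, SD 12, an illustrative cut-off of 50 and a single value per patient. None of these comes from the plan as an endpoint assumption. Repeated readings could raise the continuous power, but the documents give no correlation from which to compute by how much.

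**What to change.** In the safety subsection of the Expanded Statistical Analysis:
- Keep bradycardia and hypotension as counts by arm, and state the definition and time window used for each.
- Add a named continuous analysis of heart rate and of blood pressure, with the summary chosen in advance (for example the lowest daily value). Use the mixed model with person as random effect that the SAP already applies to longitudinal data, and report the arm difference with a 95% confidence interval.
- Say how an event comparison will be reported when an arm has no events.
- State that a non-significant event comparison will not be read as evidence of no haemodynamic effect.

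The expanded section is written in the past tense. If vital signs have already been compared by arm, the added analysis should be labelled as such and not presented as pre-specified.

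The cost is a few sentences in the SAP, extraction of vital signs from the health record, and a little more analysis. That the readings are available there is an assumption: the protocol draws clinical data from electronic records but does not list vital signs. Treatment, visits and sample size are unchanged.

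### The only collection mode specified for the 90-day mRS is an outpatient research visit, with no phone or proxy fallback, so severely disabled survivors are likely to be selectively missing from this exploratory endpoint

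*Combined protocol and SAP*

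**What the plan says.** Under Outcome Measure(s), one sentence covers all follow-up. It opens with "Follow up data will be obtained via chart review", continues with "we will obtain the mRS data at 30 days over the phone", and ends with "we will make additional outpatient follow up appointments for the research study in order to collect the NIHSS and mRS data at 90 days". Chart review is a general source and is not named as the source or backup for the 90-day mRS. No phone, caregiver, home or facility assessment is described for someone who misses that visit.

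The same section sets the status of the endpoint: "The secondary exploratory endpoints will be clinical outcomes assessed via the change in daily NIHSS and mRS at 30 and 90 days".

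On the population, Data Collection Criteria excludes "posterior circulation LVOs, NIHSS<6, CTP Penumbra <1/3 total ischemic area", so every patient starts with NIHSS of at least 6. The safety and exploratory part of the Expanded Statistical Analysis makes "hospital poor disposition (i.e. nursing home, long-term acute care hospital, or death" a planned outcome.

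On analysis, the longitudinal part of the Expanded Statistical Analysis states "For 30-day NIHSS changes (vs. baseline) and 90-day mRS changes, we used the parallel model". It adjusts for baseline NIHSS, time to thrombus removal or recanalization attempt, and percent reperfusion. It makes a general remark that mixed models need weaker assumptions about missing data. Its sensitivity analyses concern the coding of TICI and a restriction to the first five days. None addresses a missing 90-day mRS.

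**The concern.** The mRS grades the function that a person needs in order to come to a clinic. A patient who has recovered can attend. One who is bedridden or in a facility often cannot. If the visit is the only route to the score, whether a score exists depends on the score itself.

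The visit has a good reason, since NIHSS needs an examination. The mRS does not need one, and the trial already obtains it by phone at 30 days.

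At stake is the description of long-term recovery. Losing mainly mRS 4-5 makes both arms look better than they are. The 90-day change is the only mRS analysis that the plan names, and with about 80 patients a few selective losses per arm are noticeable.

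**Working it through.** The plan has no figure to reproduce. It says "We anticipate enrolling approximately 80 patients into the study" and gives no power, SD, dropout or attendance rate. Everything below is an illustration on stated assumptions, with 40 patients per arm assumed.

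**1. Main scenario, one arm.** Assumed mRS distribution and attendance, with all deaths known:

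| mRS | True % | Attendance | Observed (true × attendance) |
|---|---|---|---|
| 0-2 | 8 + 12 + 15 = 35 | 0.90 | 31.5 |
| 3 | 17 | 0.70 | 11.9 |
| 4 | 18 | 0.40 | 7.2 |
| 5 | 10 | 0.20 | 2.0 |
| 6 | 20 | 1.00 | 20.0 |
| Total | 100 | | 72.6 |

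- Observed share with mRS 0-2 = 31.5 / 72.6 = 43.4%, against a true 35%.
- Lost: 100 − 72.6 = 27.4%, about 11 of 40. Of these, (10.8 + 8.0) / 27.4 = 69% have mRS 4-5.
- Mean mRS: true 3.35, observed 232.3 / 72.6 = 3.20.

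**2. Milder scenario.** Assumed distribution 8, 12, 15, 17, 20, 12, 16%. Missing: 5% at mRS 0-3 and 20% to 40% at mRS 4-5, deaths known.

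- 20%: 33.25 / 91.0 = 36.5% with mRS 0-2; mean 3.29 becomes 3.26; 3.6 of 40 lost.
- 40%: 33.25 / 84.6 = 39.3%; mean 3.17; 6.2 of 40 lost.

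**3. Contrast between arms, deaths known.** Treated arm: the step 1 distribution with its cumulative odds multiplied by an assumed 1.6, which gives 12.2, 16.4, 17.7, 17.1, 15.5, 7.6, 13.5% and a mean of 2.84. True benefit: 3.35 − 2.84 = 0.51.

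- Same attendance in both arms: 3.20 − 2.62 = 0.58.
- Treated attendance raised to 80%, 60% and 40% at mRS 3, 4 and 5: 3.20 − 2.72 = 0.48.
- No true effect, with that same difference in attendance: treated 31.5 / 79.9 = 39.4% against control 43.4%, a gap of 4 points. The standard error at 40 per arm is √(0.394 × 0.606/40 + 0.434 × 0.566/40) = 0.11, or 11 points.
- Under milder assumptions like those of step 2, equal missingness moves a true difference of −0.31 only to about −0.32. Unequal missingness at mRS 4-5 (10-20% against 40%) with no true effect creates a difference of 0.08 to 0.12 mRS points.

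**4. Does the planned model repair it?** A likelihood-based mixed model is valid when missingness depends only on data in the model. Here attendance depends on function at 90 days. Two patients with the same baseline NIHSS, time to recanalization and reperfusion can differ in that function, and the worse one is more often absent. The covariates recover part of the loss. The 30-day mRS would recover more, but the plan does not say that it enters the 90-day analysis.

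**5. What a phone fallback would gain.** If calls reached 80% of the missed survivors in step 1 (assumed), attendance would become 98%, 94%, 88% and 84%. The observed share would be 34.3 / 94.52 = 36.3%. At 50% reached it would be 33.25 / 86.3 = 38.5%.

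**The case against.** Several points on the other side stand.

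- The endpoint is secondary and exploratory in a pilot. The primary blood markers are measured in hospital and do not depend on clinic attendance.
- No attendance rates are given, so selective loss is an inference. Nothing forbids staff from phoning a patient who misses the visit.
- The figures are unadjusted, observed-case summaries. The planned adjusted model would lose somewhat less, and the plan does not use the mRS 0-2 split.

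A reader might go further and infer that a real treatment effect could vanish or a false one appear. The documents do not support that. A large distortion of the contrast requires deaths to be missed as well. Yet chart review stands in the same sentence as the 90-day visit, deaths are a safety endpoint, and the 30-day call would reveal early deaths.

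A difference in attendance between arms is also speculative. The design is called open-label, but all patients wear the device, controls receive no current, and outcome assessment is blinded. Even when such a difference is assumed, the resulting gap is well inside its standard error.

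What remains is the missing fallback and the flattering picture of recovery that it would produce. An in-person NIHSS explains the visit, but it does not explain why a missed visit should also cost the mRS.

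**Conclusion.** The point holds in limited form. The plan specifies one route to the 90-day mRS, and the patients least able to use it are those with the worst scores. The direction of the bias follows from the design: observed recovery is too favourable. Its size rests on assumed distributions and attendance, with deaths known. Across the range tried, a true 35% with mRS 0-2 reads as 37% to 43%. The comparison between arms is affected much less, and the primary endpoints not at all. It should be corrected because the correction is cheap, not because the trial's main conclusion depends on it.

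**What to change.** In Outcome Measure(s), add after the 90-day appointment:

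> mRS at 90 days will be collected at the visit. If the visit is missed, a blinded assessor will obtain mRS by the phone interview used at 30 days, from the patient or caregiver. Deaths found by call or chart are scored mRS 6.

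Keep NIHSS in person. Record the mode of each mRS, and report missing 90-day scores by arm and by 30-day mRS. In the Expanded Statistical Analysis, add a sensitivity analysis that allows absent survivors to have worse scores than the model predicts.

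The cost is a few sentences, one data field and some extra calls by staff who already make the 30-day calls. The assessor must be blinded, because the design promises blinded outcomes. The small downside is a mixture of in-person and phone scores at 90 days, which the recorded mode lets the analyst check.

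The statistical section is written in the past tense. If follow-up is already complete, the collection change comes too late, and the missingness report and sensitivity analysis are what can still be done.
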